2.3 Sample Size and Power

A sample size of 16 subjects per treatment dose cohort with a ratio of 3:1 for MAA868 and placebo treatment assignment is based on historic data considerations. For

CONFIDENTIAL

Page 8 of 28

example, if the observed proportion of subjects in a cohort achieving target levels of inhibition is 11/12, the exact 90% confidence interval would be 0.661 to 0.996.

3. Study Endpoints

3.1 Primary Endpoint

The primary efficacy endpoint is the proportion of subjects achieving $\geq 50\%$, $\geq 80\%$, or $\geq 90\%$ inhibition of FXI ($< 50\%$, $< 20\%$, or $< 10\%$ free FXI) at trough on Day 91 at different dose levels of MAA868.

3.2 Secondary Endpoints

Efficacy

- The proportion of subjects achieving $\geq 50\%$, $\geq 80\%$, or $\geq 90\%$ inhibition of FXI ($< 50\%$, $< 20\%$, or $< 10\%$ free FXI) at trough on Day 31 and Day 61 at different dose levels of MAA868.

Safety

- All safety assessment results during the treatment and follow-up periods. Safety endpoints include:
 - Adverse Events (AE)
 - Physical exam
 - Laboratory parameters
 - Vital Signs
 - Electrocardiogram (ECG)
 - Hypersensitivity reactions
 - Injection site reactions
- Occurrence of confirmed major bleeding events, clinically relevant non-major (CRNM) bleeding events, and total bleeding events during the treatment period.
- Identification of anti-drug (MAA868) antibodies using a ligand-binding assay.

3.3 Exploratory Endpoints

Safety

Statistical Analysis Plan

Sponsor Name: Anthos

Sponsor Protocol ID: ANT-004

Covance Study ID: 000000189471

- Occurrence of major cardiovascular, cerebrovascular, systemic arterial, and venous thromboembolic events (VTEs).
- Concentrations of D-dimer and other exploratory thrombogenesis markers during the treatment period.

4. Pharmacokinetic/Pharmacodynamic Variables

4.1 Pharmacokinetic Analysis

PK samples will be obtained and evaluated at all post-screening visits (where data permit) in all subjects at all dose levels using the actual recorded sampling times. Untreated (placebo) samples will not be analyzed. All concentrations below the lower limit of quantitation (LLOQ) or missing data will be labeled as such in the concentration data listings.

The concentration-times courses of abelacimab will be tabulated for each sampling interval. Individual and geometric mean concentration vs time curves of MAA868 (using the actual sampling times for individual plots and the planned sampling intervals for mean plots) will be plotted using both linear and semilogarithmic scale.

The following pharmacokinetic parameters will be estimated, where data permit, from the plasma concentrations of total MAA868 following the Day 61 dose administration using noncompartmental methods in validated software program Phoenix WinNonlin (Certara, Version 8.1 or higher):

Parameter	Units ^a	Definition
AUC _{last}	h*µg/mL	area under the concentration-time curve from time 0 to the time of the last quantifiable concentration ^b
C _{max}	µg/mL	maximum observed concentration within the postdose concentration-time profile ^c
C _{min}	µg/mL	minimum observed concentration within the postdose concentration-time profile
DAUC _{last}	h*µg/mL/mg	AUC _{last} normalized by dose administered ^d
DC _{max}	µg/mL/mg	C _{max} normalized by dose administered ^d

^a Units are based on concentration units (provided by the bioanalytical lab or preferred units for presentation of PK parameters) and dose units used in the study.

^b Area under the concentration-time curve will be calculated using the linear trapezoidal rule for increasing and decreasing concentrations

^c Due to the sparse sampling, this may not directly correspond to the C_{max} of MAA868 determined with intensive sampling schemes.

^d Calculated by dividing the parameter by the dose (mg)

Additional PK parameters may be determined where appropriate.

CONFIDENTIAL

Page 10 of 28

Document Date: 18-MAR-2021

ST-AD-008 version 05

Statistical Analysis Plan

Sponsor Name: Anthos
Sponsor Protocol ID: ANT-004

Covance Study ID: 000000189471

Pharmacokinetic analysis will be carried out where possible using actual blood sampling times postdose. If an actual time is missing, the sample concentration result will be treated as missing unless there is scientific justification to include the result using the nominal time.

The parameters C_{max} and C_{min} will be obtained directly from the concentration-time profiles.

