ISTH	International Society of Thrombosis and Haemostasis
IN	investigator notification
MedDRA	Medical Dictionary for Regulatory Activities
PAF	paroxysmal atrial fibrillation
PD	pharmacodynamic
PK	pharmacokinetic
QTcF	QT interval corrected by Fridericia formula
RBC	red blood cells
SAE	serious adverse event
SAP	statistical analysis plan
s.c.	subcutaneous
sCr	serum creatinine
sCT	spiral computed tomography
SD	standard deviation
SOC	system organ class (MedDRA classification)
SUSAR	suspected unexpected serious adverse reaction
TEAE	treatment-emergent adverse event
VTE	venous thromboembolism
WBC	white blood cells
WHO	World Health Organization

PHARMACOKINETIC DEFINITIONS AND SYMBOLS

AUC _{0-t}	The area under the plasma concentration-time curve from time zero to time 't' where t is a defined time point after administration [mass x time / volume]
AUC _{inf}	The area under the plasma concentration-time curve from time zero to infinity [mass x time / volume]
AUC _{last}	The area under the plasma concentration-time curve from time zero to the time of the last quantifiable concentration [mass x time / volume]
C ₀	The initial concentration at the end of an intravenous infusion
CL	The systemic clearance following intravenous administration
C _{max}	The observed maximum plasma concentration following subcutaneous drug administration [mass / volume]
F	Bioavailability
T _{1/2}	The terminal elimination half-life [time]
T _{max}	The time to reach the maximum concentration after drug administration [time]
V _{ss}	The steady state volume of distribution following intravenous administration

GLOSSARY OF TERMS

Assessment	A procedure used to generate data required by the study
Cohort	A specific group of subjects fulfilling certain criteria
Dosage	Dose of the study treatment given to the subject in a time unit
Enrollment	Point/time of subject entry into the study at which informed consent must be obtained (i.e. prior to starting any of the procedures described in the protocol)
Healthy volunteer	A person with no known significant health problems who volunteers to be a study participant
Investigational drug	The study drug whose properties are being tested in the study; this definition is consistent with US CFR 21 Section 312.3 and Directive 2001/20/EC and is synonymous with “investigational new drug” or “test substance”
Screen Failure	A subject who is screened but is not treated or randomized
Subject	A trial participant

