5.5. Treating the subject

MAA868 will be administered to the subject by study staff via s.c. administration. See the Pharmacy Manual for further details.

Sponsor qualified medical personnel will be readily available to advise on trial related medical questions or problems.

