7.13 Pharmacokinetic Analysis

The PK samples will be collected at the timepoints defined in the Assessment schedule (Table 9). Follow instructions outlined in the Central Laboratory Manual regarding sample collection, numbering, processing and shipment. See Section 7.15 regarding the potential use of residual samples.

In order to better define the PK profile, the timing of the PK sample collection may be altered based on emergent data. The number of samples/blood draws and total blood volume collected will not exceed those stated in the Laboratory Manual. Changes to the PK Assessment schedule, if any, will be communicated to the sites in the dose adjustment minutes.

The PK samples will be obtained and evaluated in all subjects at all dose levels. Untreated (placebo) samples will not be analyzed.

Concentrations of plasma total MAA868 (i.e. MAA868 that is bound to FXI or not bound to FXI) will be determined by a validated LC-MS/MS method. A detailed description of the method used to quantify the concentration of total MAA868 will be included in the bioanalytical raw data and in the Bioanalytical Data Report.

All concentrations below the LLOQ or missing data will be labeled as such in the concentration data listings.

For standard PK abbreviations and definitions see the list provided at the beginning of this protocol.

The following PK parameters will be determined, where data permit, using the actual recorded sampling times and non-compartmental method(s) with Phoenix WinNonlin (Version 6.2 or higher): C_0 (the concentration at the end of infusion), AUC_{last} , AUC_{inf} , C_0/D , and AUC/D , based on the plasma concentration data.

The linear trapezoidal rule will be used for AUC calculation. The terminal half-life of MAA868 ($T_{1/2}$), volume of distribution (V_{ss}) and clearance (CL) will also be estimated, if feasible, based on the data.

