7.10 Interim Analysis

After approximately 10 of the subjects in cohort 1 have received their second dose of study drug and have been followed for at least an additional 14 days, the safety and tolerability data (AEs, laboratory assessments, vital signs and ECGs) will be evaluated by the Sponsor's Medical Monitor and Covance Lead Project Physician. The decision to proceed to cohort 2 will be made only after:

- It is confirmed that the cohort 1 dose was safe and tolerated
- At least half of the subjects in cohort 1 have been randomized

If notable AEs or safety concerns are found in cohort 1, the study may be terminated.

Likewise, after approximately 10 of the subjects in cohort 2 have received their second dose of study drug and have been followed for at least an additional 14 days, safety, tolerability, and other analyses will be evaluated.

8. Changes in Planned Analysis

There are no changes from planned analyses in the protocol.

9. Data Issues

There are no data issues to report.

10. References

- 1 ICH. *ICH E3 Guideline: Structure and Content of Clinical Study Reports Questions & Answers*, 2012.
- 2 SAS Institute. *SAS/STAT Software*: Cary, NC: SAS Institute; 2003.

Statistical Analysis Plan

Sponsor Name: Anthos
Sponsor Protocol ID: ANT-004

Covance Study ID: 000000189471

11. Appendices

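### DAUClast divides an AUC that includes carry-over from two earlier doses by one dose, so it is neither per-interval nor per-mg exposure; the SAP's changes to the protocol's PK list are undeclared

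*SAP*

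**What the plan says.** **Protocol.** Section 7.13 (Amendment 2; the list is the same in Amendment 1, the version the SAP cites) names C0, described as "the concentration at the end of infusion", with AUClast, AUCinf, C0/D and AUC/D. It adds that half-life, Vss and CL "will also be estimated, if feasible, based on the data". The protocol's PK definitions give C0 as "The initial concentration at the end of an intravenous infusion" and CL as "The systemic clearance following intravenous administration"; Vss is defined in the same intravenous terms. Yet section 5.5 says "MAA868 will be administered to the subject by study staff via s.c. administration".

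**SAP.** Section 4.1 lists AUClast, Cmax, Cmin, DAUClast and DCmax, estimated "from the plasma concentrations of total MAA868 following the Day 61 dose administration using noncompartmental methods". AUClast ends at the last quantifiable concentration. DAUClast is AUClast "normalized by dose administered", and a footnote makes clear that the divisor is the dose in mg. An open clause allows further parameters without naming any. Section 8 states: "There are no changes from planned analyses in the protocol".

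**Schedule.** Doses are given on Days 1, 31 and 61. PK samples from the third dose on are Day 61 predose and Days 71, 91, 101, 121 and 170 (protocol Table 9).

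**The concern.** A dose-normalised AUC is normally read as exposure per mg. That reading works for a single-dose AUCinf divided by the dose, or for the AUC over one dosing interval near steady state divided by the dose. DAUClast is neither. Its numerator starts at the third dose, when drug from two earlier doses is still present, and runs through the whole washout, while its denominator counts one dose. Its size also depends on when a subject falls below the LLOQ.

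The same long profile affects Cmin. The lowest concentration after the Day 61 dose will normally be the last quantifiable washout sample, not the trough before a next monthly dose.

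At stake is whether the tabulated PK parameters mean what their labels suggest. Protocol 1.2 says that the study will help choose doses for phase 3, and its title puts PK first. As listed, the SAP prespecifies neither exposure over a dosing interval nor a half-life in patients with AF, and section 8 does not tell the reader that the list has changed.

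**Working it through.** **Interval.** SAP 2.2 gives a 110-day washout. Nominally 170 − 61 = 109 days, which agrees.

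**Inputs.** Dosing and sampling days are as above. Protocol 1.1 gives a mean half-life of 20 to 28 days and a median time of Cmax on Day 7 to 21. That is 6-20 or 7-21 days after dosing, depending on how the day is counted, so 6-21 is used.

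**Model (assumption).** Linear one-compartment, first-order absorption, three equal doses on time. k = ln 2 / half-life; ka solves Tmax = ln(ka/k)/(ka − k). With single-dose AUCinf set to 1, the share of a dose's area still to come t days after it is

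R(t) = [ka·exp(−kt) − k·exp(−ka·t)] / (ka − k).

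Relative to single-dose AUCinf/D:

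- DAUClast to Day 170 = [1 − R(109)] + [R(30) − R(139)] + [R(60) − R(169)], for the third, second and first dose
- DAUClast to Day 121 = 1 + R(30) − R(90) − R(120)
- AUC over Day 61-91 per dose = 1 − R(90)

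**Low corner (half-life 20, Tmax 6).** k = 0.0347, ka = 0.469. R(30) = 0.382, R(60) = 0.135, R(90) = 0.048, R(109) = 0.025, R(120) = 0.017, R(139) = 0.009, R(169) = 0.003.
- To Day 170: 0.975 + 0.373 + 0.132 = 1.48; earlier doses supply 0.505/1.48 = 34%.
- To Day 121: 1 + 0.382 − 0.048 − 0.017 = 1.32.
- Day 61-91: 1 − 0.048 = 0.95.

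**High corner (half-life 28, Tmax 21).** k = 0.0248, ka = 0.081. R(109) = 0.097, R(30) = 0.646, R(139) = 0.046, R(60) = 0.322, R(169) = 0.022.
- To Day 170: 0.903 + 0.600 + 0.300 = 1.80; earlier doses supply 0.900/1.80 = 50%.

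| Half-life / Tmax (d) | to Day 170 | to Day 121 | Day 61-91 | from earlier doses |
|---|---|---|---|---|
| 20 / 6 | 1.48 | 1.32 | 0.95 | 34% |
| 20 / 21 | 1.78 | 1.47 | 0.91 | 46% |
| 28 / 6 | 1.62 | 1.33 | 0.89 | 43% |
| 28 / 21 | 1.80 | 1.42 | 0.85 | 50% |

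These are exact integrals. The planned linear trapezoid on the scheduled days gives 1.46-1.82 to Day 170 for Tmax 7-21. On Days 61, 71 and 91 alone it reads about 4-9% low.

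**Cmin.** From Day 91 to Day 170 is 79 days. Decay at the half-life alone leaves 2^(−79/20) = 6% to 2^(−79/28) = 14% of the Day 91 concentration. If Day 170 is quantifiable, that value is Cmin.

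**Half-life.** Days 91, 101, 121 and 170 span 79 days, or 79/28 = 2.8 to 79/20 = 3.95 half-lives, and all lie at least 30 days after the last dose. A log-linear fit in the noise-free model (Tmax 7-21) returns 20.0-22.9 days for a true 20 and 28.0-29.6 for a true 28. The worst error is 2.9/20, about 14%.

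**Lists side by side.** In protocol 7.13 but not in SAP 4.1: C0, C0/D, AUCinf, half-life, Vss, CL. In SAP 4.1 but not in protocol 7.13: Cmax, Cmin, DCmax. Section 8 of the SAP records none of this.

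**The case against.** The strongest case is that little follows from the defect, and much of that case stands.

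- *A reader might infer that parameters that cannot be obtained will be computed.* They will not. The SAP does not carry over C0, C0/D, Vss or CL; what remains is stale protocol text.
- *A reader might infer that the half-life goes unexamined.* The protocol made it conditional on feasibility, and the SAP's open clause still allows it. Concentrations are plotted on a semilogarithmic scale (SAP 4.1) and summarised by visit and listed (SAP 7.9). The decline will be visible; only a prespecified, tabulated half-life is missing.
- *A reader might infer that the drug will appear more slowly cleared than in the single-dose studies, or that dose selection will be harmed.* Neither document plans to compare DAUClast with those studies or to derive CL/F from it. Protocol 3.3 points to a PK/PD model for dose selection, and such a model would ordinarily use individual concentrations.
- *Carry-over cancels between 120 mg and 180 mg.* It does under linear PK, with three on-time doses and equal last quantifiable times. Protocol 5.6 permits interruptions, so these conditions are not guaranteed. The cancellation also does not rescue the value as exposure per mg.
- *The ±10-day window at end of study.* It moves AUClast by only about −2.6% to +2.0% in the model. The last quantifiable day matters more, but no LLOQ is given, so whether it varies is unknown.
- *AUCtau is fragile.* It rests on three samples, and the Day 91 window of ±2 days alone moves it by about 5-6%. This is a reason to keep AUClast beside it, not to leave DAUClast as the only dose-normalised AUC.

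**Conclusion.** The point holds as a defect of definition and of disclosure. DAUClast, as written, cannot be read as exposure per interval or per mg. In the assumed model it is about 1.5-1.8 times single-dose AUCinf/D when Day 170 is quantifiable, with about 34-50% of the area coming from earlier doses, and about 1.3-1.5 times when Day 121 is the last quantifiable sample. AUC over Day 61-91 per dose is 0.85-0.95 of the same reference, which makes it the interpretable quantity. Cmin is mislabelled in effect. The no-changes statement in SAP section 8 is incorrect whatever the model.

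The factors rest on linear kinetics, healthy-subject half-life and Tmax, and three equal doses on time; target-mediated or otherwise nonlinear kinetics would change them. PK parameters are descriptive and do not enter the primary endpoint, which is free FXI at trough. The documents do not support a claim that the primary result or the dose decision is compromised. The change is worth making because it is cheap and removes a misleading summary.

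**What to change.** In SAP 4.1:

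- Add AUCtau over Day 61-91 from actual sampling times, stating how it is standardised to 30 days when the Day 91 visit is early or late (for example, by interpolation with the neighbouring sample).
- Use AUCtau/dose in place of DAUClast as the dose-normalised exposure. Keep AUClast as a descriptive multi-dose measure, labelled as such.
- Restrict Cmin to Day 61-91, or report the Day 91 trough.
- Add apparent terminal half-life from quantifiable Day 91-170 samples, with at least three points.

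In protocol 7.13, replace the intravenous parameters with ones that suit s.c. dosing. In SAP section 8, record every difference from the protocol list.

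The cost is wording and additional noncompartmental output from samples already scheduled. The drawback is that AUCtau has three samples per subject, reads about 4-9% low by linear trapezoid in the model, and under the SAP 4.1.1 criteria is lost if Day 71 is missing or the maximum falls on Day 91. Retaining AUClast covers those cases.

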MAA868 was evaluated in a first-in-human (FIH) study (CMAA868X2101) to characterize its safety/tolerability, pharmacokinetics (PK) and pharmacodynamics (PD) in healthy subjects following single s.c. administration. In total, 6 cohorts with 10 subjects each (8 MAA868: 2 Placebo) were enrolled. The doses of MAA868 administered in Cohorts 1 to 5 ranged from 5 mg to 240 mg. In a sixth cohort, 240 mg of MAA868 was administered to subjects with body mass index (BMI \geq 35 kg/m²).

In the FIH study, MAA868 appeared to be safe and well tolerated, and the incidence of AEs were comparable across dose groups and placebo. No bleeding events, hypersensitivity reactions or injection site reactions were reported. Exposure increased with increasing dose of s.c. MAA868; the median maximum observed concentration (C_{max}) occurred on Day 7 to 21 and the mean terminal elimination half-life ranged from 20 to 28 days. A dose and time-dependent prolongation of aPTT occurred with MAA868 after single s.c. administration; the 150 mg dose resulted in a mean aPTT prolongation \geq 2-fold at Day 29. Doses greater than 150 mg extended the duration of aPTT prolongation but did not produce a greater prolongation of aPTT. Robust and sustained reductions of free FXI \geq 90% were observed with 150 mg MAA868 at Day 29 and up to Day 43 with 240 mg. A high BMI was associated with a lower MAA868 exposure and slightly shorter duration of aPTT prolongation. Robust reductions in free FXI and in FXI coagulation activity and relevant aPTT prolongation are predicted to occur within 12 to 24 hours after MAA868 s.c. administration with relevant clinical doses.

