12.4. Appendix 4 - Schedule of Assessments

Table 9: Schedule of Assessments

Period	Screening	Treatment							Washout / Follow-up			
Visit	1	2	3	4	5	6	7	8	9	10	TD	EoS
Day	-28 to -3	1 (predose)	11	31 (predose)	41	61 (predose)	71	91	101	121	-	170
Window			±2	±2	±3	±2	±3	±2	±3	±3		±10
Informed consent	X											
Medical history	X											
Drug & alcohol screen	X											
I/E criteria	X	X										
Physical Exam	X	X	X	X		X		X		X	X	X
Height	X											
Weight	X	X										X
Vital signs	X	X	X	X	X	X	X	X	X	X	X	X
12-lead ECG	X	X						X				X
HIV, Hepatitis B, Hepatitis C	X											
aPTT, Free and total FXI	X	X	X	X	X	X	X	X	X	X	X	X
aPTT (corrected for FXI), FXI:C		X				X		X				X
PK assessment: total MAA868		X	X	X	X	X	X	X	X	X		X
Antidrug antibodies (ADA)		X		X		X	X	X		X		X
Exploratory biomarker collection	X	X		X		X		X		X		
Complete safety Labs	X	X	X	X	X	X		X		X	X	X
Pregnancy test	Serum	Urine			Urine			Urine			Urine	Urine
Urine	X	X	X	X	X	X		X		X	X	X
Fecal occult blood test	X	X										
AE collection						X						
Concomitant meds						X						
Local assessment of CV and cerebrovascular events							X					
Local assessment of bleeding events							X					
Dispense Study Medications		X		X		X						
Drug Accountability		X		X		X		X				
MAA868		X		X		X						
Placebo		X		X		X						

Period	Screening	Treatment							Washout / Follow-up			
Visit	1	2	3	4	5	6	7	8	9	10	TD	EoS
Day	-28 to -3	1 (predose)	11	31 (predose)	41	61 (predose)	71	91	101	121	-	170
Window			±2	±2	±3	±2	±3	±2	±3	±3		±10
Injection site inspection (post-dose)		X	X	X	X	X	X					
Study disposition								X			X	X

TD = Study treatment discontinuation; EoS = End of Study; FXI:C = Factor XI coagulation activity

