4.1.1 Criteria for Calculation and Reporting of Area Under the Concentration-time Curve

The minimum requirement for the calculation of area under the concentration-time curve (AUC) will be the inclusion of at least 3 consecutive concentrations above the lower limit of quantification. If there are only 3 consecutive concentrations, at least 1 should follow C_{max} .

4.1.2 Criteria for Handling Missing or Concentrations Below the Limit of Quantification in Pharmacokinetic Analysis

Plasma concentrations below the limit of quantification (BLQ) will be assigned a value of 0 before the first measurable concentration and thereafter BLQs will be treated as missing. The following rules apply with special situations defined below:

- If an entire concentration-time profile is BLQ, it will be excluded from PK analysis.
- Where 2 or more consecutive concentrations are BLQ at the end of a profile, the profile will be deemed to have terminated and any further quantifiable concentrations will be set to missing for the calculation of the PK parameters, unless they are considered to be a true characteristic of the profile of the drug.

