7.9 Pharmacokinetic/Pharmacodynamic Analysis

Individual MAA868 plasma concentrations and PD parameters are evaluated for the PK/PD set and will be summarized by treatment group for each scheduled collection visit/timepoint. PK parameters (listed in [section 4](#)) are evaluated for the PK/PD set and will be summarized by treatment group for the MAA868 arms only. Standard descriptive statistics (see [Table 1](#)) will be presented for the observed values. Individual MAA868 plasma concentrations and all PK parameters will be listed for each subject by treatment group.

Concentrations below the LLOQ will be treated as zero in summary statistics and for PK parameter calculations. A geometric mean will not be reported if the dataset includes zero values.

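### The SAP's Cmin has no end time, so it picks up the last washout sample and not the Day 91 trough; and the SAP gives two incompatible BLQ rules for PK parameters

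*SAP*

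**What the plan says.** SAP 4.1 estimates the PK parameters from total MAA868 concentrations "following the Day 61 dose administration using noncompartmental methods" and defines Cmin as the "minimum observed concentration within the postdose concentration-time profile". The closing text of SAP 4.1 adds that Cmax and Cmin are read straight from the profiles. It gives no dosing interval, last day or Day 91 limit.

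Day 61 is the third and final dose (SAP 2.2). In the protocol's Table 9 (Appendix 4), the row "PK assessment: total MAA868" has samples after that dose on Days 71, 91, 101, 121 and 170. The windows are ±2 days at Day 91 and ±10 days at Day 170. The treatment-discontinuation visit has no PK sample.

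On BLQ values, SAP 4.1.2 says they "will be assigned a value of 0 before the first measurable concentration and thereafter BLQs will be treated as missing". SAP 7.9 says: "Concentrations below the LLOQ will be treated as zero in summary statistics and for PK parameter calculations". It adds: "A geometric mean will not be reported if the dataset includes zero values". Protocol 8.7 has the same zero rule as SAP 7.9. SAP section 8 reports no departure from the protocol's planned analyses.

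**The concern.** A reader of a multiple-dose PK table will take Cmin as the concentration at the end of the dosing interval. As defined, it is a washout concentration. The same report would show a Cmin many times lower than the Day 91 concentration. The arm summaries would also pool values taken at different times after the last dose, so part of the between-subject variation would reflect visit timing and missed visits. The study is meant to help choose a phase 3 dose (protocol 1.2), so mistaking this Cmin for trough exposure would matter.

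The BLQ conflict adds to this, because late washout samples are where BLQ values are most likely. Two programmers who each follow the SAP could report different Cmin values for the same subject.

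**Working it through.** **Inputs**
- Last dose Day 61; trough Day 91; later PK samples on Days 101, 121 and 170 (protocol Table 9, SAP 2.2).
- Half-life: "the mean terminal elimination half-life ranged from 20 to 28 days" (protocol 1.1; single doses in healthy subjects). Median time of Cmax was Day 7 to 21 in the same study.
- 12 active subjects per cohort (protocol 5.3).

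**The plan's own intervals.** 170 − 91 = 79 days, as stated in SAP 2.2. 170 − 61 = 109 days, against the stated 110.

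**Which sample is the minimum?** A one-compartment model with first-order absorption (an assumption) was run for doses on Days 1, 31 and 61, with half-lives of 20, 24 and 28 days and single-dose times of Cmax of 7, 14 and 21 days. The minimum falls on Day 170 in all 9 combinations. Day 91 is 6.2 to 15.5 times Day 170. Between Days 71 and 91 alone, the lower value is Day 91 in all 9.

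**Size by simple decline**, ratio = 2^(−d / half-life):

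| Comparison | d (days) | Half-life 20 d | Half-life 28 d |
|---|---|---|---|
| Day 170 / Day 91 | 79 | 0.065 (15.5-fold lower) | 0.141 (7.1-fold lower) |
| Day 121 / Day 91 | 30 | 0.354 | 0.476 |
| Day 121 / Day 170 | 49 | 5.46 | 3.36 |
| Day 160 / Day 180 (largest gap in the ±10 d window) | 20 | 2.00 | 1.64 |
| Day 89 / Day 93 (largest gap in the ±2 d window) | 4 | 1.15 | 1.10 |

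The last three rows show the earlier day over the later one, 2^(d / half-life).

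**One of 12 subjects has no Day 170 sample.** That subject's Cmin becomes the Day 121 value. Arm mean relative to Day 91, with otherwise identical subjects:
- 20 d: (11 × 0.0647 + 0.3536) / 12 = 0.089, against 0.065: +37%.
- 28 d: (11 × 0.1415 + 0.4758) / 12 = 0.169, against 0.141: +20%.

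**One of 12 subjects is BLQ at Day 170** (an assumption; the documents give neither the LLOQ nor a frequency).
- SAP 4.1.2: the value is missing and Cmin falls back to Day 121. The arm mean is 0.089 or 0.169, as above.
- SAP 7.9 and protocol 8.7: Cmin is 0. The arm mean is 11 × 0.0647 / 12 = 0.059, or 11 × 0.1415 / 12 = 0.130, and no geometric mean is reported for the arm, although SAP 7.1 Table 1 plans one.
- Ratio between the rules: 1.50 (20 d) or 1.31 (28 d).

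**Could the profile be meant to stop at Day 91?** The text points the other way. SAP 4.1 evaluates PK samples at all post-screening visits. The rule in SAP 4.1.2 for ending a profile needs two consecutive BLQ values with further quantifiable values after them, hence at least three postdose samples. Days 61 to 91 hold only two after the dose. The on-treatment limit of 30 (±5) days in SAP 6.1 applies to trough FXI, not to MAA868.

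**The case against.** The SAP never calls Cmin a trough. Cmax is defined over the same profile and AUClast also runs to the last quantifiable value, so the parameters follow one consistent convention. Cmin is not among the parameters in protocol 7.13, and no objective, endpoint or cohort decision uses it. Concentrations "will be summarized by treatment group for each scheduled collection visit/timepoint", so the Day 91 value is reported anyway, and SAP 4.1 allows further parameters to be added. The figures rest on healthy-subject half-lives; the window spread is a maximum, and the missing-sample and BLQ cases are conditional. On a declining profile, trailing BLQ values cannot change Cmax, AUClast or their dose-normalised forms.

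Much of this stands, and it limits the size of the point. Cmin is under-specified; it does not contradict a stated intent. The BLQ conflict reaches only one of the five listed parameters when the profile declines. The fallback to Day 121 for a BLQ sample holds only under SAP 4.1.2. But consistency with the other parameters does not make a minimum over an open-ended washout interpretable, and tabulating Day 91 elsewhere does not stop the parameter table from showing a misleading figure. The clash between the BLQ rules is in the text whether or not a BLQ value occurs.

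**Conclusion.** Both parts hold. As written, Cmin is the last washout sample: about 7 to 15 times below Day 91 under simple decline, and about 6 to 15 times below in the absorption model. It depends on follow-up timing, by up to 1.6- to 2.0-fold within the Day 170 window and 3.4- to 5.5-fold if that sample is missing. The SAP also gives two incompatible BLQ rules for PK parameters with no order of precedence, and SAP 4.1.2 is an undeclared departure from protocol 8.7. The sizes assume monotone decline at the stated mean half-lives. The BLQ figures also assume that such a value occurs. The primary and secondary efficacy results are unaffected because they use free FXI at the trough visits. This should be corrected, but it does not threaten the trial's main conclusions.

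**What to change.** - **SAP 4.1:** replace Cmin with Ctrough, the Day 91 concentration, missing if there is no Day 91 sample. Alternatively, limit Cmin to the Day 61–91 dosing interval; in all 9 modelled cases that gives the Day 91 value.
- **BLQ:** keep one rule for PK parameter calculations. One option is to keep SAP 4.1.2, remove PK parameter calculations from the zero rule in SAP 7.9 so that zero applies to concentration summaries only, and list the departure from protocol 8.7 in SAP section 8. The other is to align SAP 4.1.2 with protocol 8.7, which leaves no departure to list.

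The cost is wording in SAP 4.1 and in 7.9 or 4.1.2, plus one entry in section 8 under the first option. No new samples or visits are needed.
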